Prior to enrolment, all patients will be asked to sign an informed consent form to document that they understood the scope of the study (including procedures, follow-up evaluations, and any potential risks involved), were allowed an opportunity to ask questions pertaining to this study and were apprised of treatment alternatives. The study is open to qualifying patients without regard to sex or race.

Sample size

In this study, the primary comparison is the effectiveness of different bone substitutes in maintaining bone volumes, therefore, the sample size calculation will be based on bone volumes. To detect a difference of 5 mm³ in bone volume changes between the two bone substitutes (standard deviation of 6.96 mm³(3)) with a two-side 5% significance level and a power of 80%, a total sample size of 80 patients will be necessary, given an anticipated dropout rate of 20%. We can contribute with 50 patients (25 per group).

Outcome measures

Primary outcome variable

Volume changes of the volume changes of the peri-implant tissues will be evaluated by taking a limited view cone-beam computed tomography (CBTC) of the area of interest at implant placement, 1 and 5 years after loading.

Secondary outcome variables

Crown/implant failure: whether it will not be possible to place the crown because of implant failure or secondary to implant failure, and replacement of the crown for any reason. Implant failure is defined as implant mobility and/or any infection dictating implant removal and any mechanical complications rendering the implant unusable (e.g. implant fracture). The stability of each individual implant will be measured by the blinded outcome assessor manually by assessing the stability of the crown using the handles of two metallic instruments at 1 and 5 years after loading.

Biological and biomechanical complications: will be recorded and reported by study group. Examples of biological complications are: fistula, peri-implantitis. Examples of biomechanical complications are fracture of the metal screws, loosening of the crown, fracture of the ceramic lining.

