An impression with the pick-up impression copings will be made with a polyether material. Within 2 weeks, a definitive metal-ceramic screw-retained crown will be delivered on definitive titanium abutments.

- Periapical radiographs must be made. If the peri-implant marginal bone levels are not readable a second radiograph must be taken.
- Buccal and occlusal pictures of the implant including one adjacent tooth per side must be made.

1 year after loading (APPENDIX 2):

- Crowns will be manually tested for stability.
- Periapical radiographs must be made. If the peri-implant marginal bone levels are not readable a second radiograph must be taken.
- Buccal and occlusal pictures of the implant including one adjacent tooth per side must be made.
- A limited view CBCT of the study implant must be taken.

5 years after loading (APPENDIX 2):

- Crowns will be manually tested for stability.
- Periapical radiographs must be made. If the peri-implant marginal bone levels are not readable a second radiograph must be taken.
- Buccal and occlusal pictures of the implant including 1 adjacent tooth per side must be made.
- A limited view CBCT of the study implant must be taken.

All patients will be recalled every 6 months for professional maintenance. If necessary, the number of maintenance visits can be increased.

In case of suspected implant loss, peri-implantitis, fistula, etc., observed during any of the scheduled visit or during an emergency visit, intraoral radiographs and clinical pictures must be taken and the “Complications, protocol deviation and drop-out CRF” (APPENDIX 3) should be filled in.

Time

Day 1	photos/extraction/implant placement/patient inclusion/photos/group allocation/augmentation/impression/rx/CBCT
Within week 2	definitive crown delivery/photos
1 year after loading	implant stability/impressions/rx/CBCT/photos/maintenance
5 years after loading	implant stability/impressions/rx/CBCT/photos/maintenance

Drop-outs

All drop-outs should be reported and the reason for dropping out should be investigated and reported per study group. No included patient can be excluded for any reasons by the clinical investigators.

Statistical analysis

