All data analysis will be carried out according to a pre-established analysis plan by a dentist with expertise in statistics blinded to group allocation. Descriptive statistics will be performed using mean and standard deviation for quantitative data and frequency and percentage for qualitative data. All-important harms or unintended effects in each group will be reported. The statistical unit of the analysis will be the patient. The primary outcome variable will be volume changes between baseline and 1- and 5-year after augmentation.

For volumetric analysis, an intra-rater agreement study will be performed on the operator to test his reliability. A set of 20 volumetric changes will be evaluated twice with a two-week interval between the measurements. The operator will be considered reliable if the intraclass coefficient of correlation is greater than 0.75.

A comparison of the baseline characteristics between groups will be presented. Differences in the proportion of dichotomous outcomes (e.g. prosthesis and implant failures, complications) will be compared between the groups using a chi-square test. Mean differences between groups for continuous outcomes (e.g. peri-implant marginal bone level changes, PES scores and volumetric analysis) will be compared using an independent sample t-test for pairwise comparisons. Comparisons between each time points and the baseline measurements will be made by paired t-tests, to detect any changes in marginal peri-implant bone levels for each study group.

All statistical comparisons will be conducted at the 0.05 level of significance and estimate, standard error, 95% confidence intervals and P-value will be reported for each term of the models.

In the case of early implant failure or complication the volumetric change will be measured anyway.

The statistical analysis will be intention-to-treat and deviation from the protocol will be considered according to the randomization scheme: all participants will be included in the analysis regardless of adherence to the protocol. In any case, if large deviations from the protocol are generated, a sensitivity per-protocol analysis will be performed.

Administrative procedures and data management

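### Cheap improvement for the 5-year volume contrast: the named t-test, without imputation, makes no use of the 1-year CBCT of patients lost later; a two-visit model would

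*Protocol*

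**What the plan says.** All of this is in the protocol; no separate analysis plan is shown.

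- **Test.** Under Statistical analysis, continuous outcomes, with the volumetric analysis among the examples, "will be compared using an independent sample t-test for pairwise comparisons".
- **Outcome.** The same section states: "The primary outcome variable will be volume changes between baseline and 1- and 5-year after augmentation".
- **Scans.** The follow-up list for 1 year after loading includes: "A limited view CBCT of the study implant must be taken". The 5-year list has the same item.
- **Size and dropout.** The Sample size section takes a difference of 5 mm³, an SD of 6.96 mm³, two-sided 5% and 80% power, and concludes that "a total sample size of 80 patients will be necessary, given an anticipated dropout rate of 20" per cent. It adds that 50 patients, 25 per group, can be contributed.
- **Analysis set.** The analysis is intention-to-treat: "all participants will be included in the analysis regardless of adherence to the protocol".
- **Losses.** Under Drop-outs: "All drop-outs should be reported and the reason for dropping out should be investigated and reported per study group". Under Statistical analysis: "In the case of early implant failure or complication the volumetric change will be measured anyway". No method for a missing 5-year volume is named.
- **Models.** The section also promises that a "P-value will be reported for each term of the models", although the only comparisons it names are t-tests and a chi-square test.

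**The concern.** Four years separate the two follow-up scans, and the protocol expects one patient in five to be lost. A patient scanned at 1 year and lost later has a valid measurement of the primary outcome. A t-test on observed 5-year values cannot use it.

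Two things are at stake. The first is some precision at 5 years. The second is a stronger missing-data assumption than necessary: the completer comparison needs loss to be unrelated to the outcome. A model on both visits needs it to be unrelated only after allowing for what was seen at 1 year. Because the protocol itself names the test for its primary outcome, this is a choice it makes and not merely a detail left open.

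**Working it through.** **Inputs.** From the Sample size section: difference 5 mm³, SD 6.96 mm³, two-sided 5%, 20% dropout, 80 patients (40 per arm), and 25 per group contributed. Assumed, because the protocol does not give them: a 1-year/5-year correlation ρ of 0.5 to 0.8, and the timing and cause of dropout.

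**1. The plan's own figure.** By the exact (noncentral t) calculation, power is 79.5% at 31 per arm and 80.8% at 32. Then 32 / 0.8 = 40 per arm, or 80 in total. The planned size is reproduced.

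**2. The t-test at 5 years.** With n5 patients per arm scanned at 5 years, variance = 2·SD²/n5 = 96.88/32 = 3.028. The SE is 1.74 mm³, the 95% CI half-width 3.48 mm³ and power 81%.

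**3. The two-visit model.** It estimates each arm's 5-year mean as the completers' mean, shifted by the regression slope times the gap between the 1-year mean of everyone scanned and that of completers. With n1 per arm scanned at 1 year:

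variance = 2·SD²·[(1−ρ²)/n5 + ρ²/n1]

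For n1 = 40, n5 = 32, ρ = 0.5: 96.88 × (0.75/32 + 0.25/40) = 2.876, SE 1.696, ratio to the t-test 0.950. For ρ = 0.8: 96.88 × (0.36/32 + 0.64/40) = 2.640, SE 1.625, ratio 0.872.

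| 40 per arm, 20% lost at random | Variance ratio, ρ 0.5 / 0.8 | Power, ρ 0.5 / 0.8 |
|---|---|---|
| t-test | 1 | 80.8% |
| Model, all dropouts scanned at 1 year (n1 = 40) | 0.950 / 0.872 | 82.7% / 85.7% |
| Model, half scanned (n1 = 36) | 0.972 / 0.929 | 81.8% / 83.5% |
| Model, none scanned (n1 = 32) | 1.00 / 1.00 | no gain |

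The first model row is worth 33.7 to 36.7 completers per arm instead of 32. Simulation agrees (power 82.3% and 85.7%). In simulation the half-width falls from 3.48 to 3.26–3.42 mm³ if all dropouts were scanned, and rises to 3.49–3.50 if none were.

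**4. At 25 per arm (20 completers).** t-test: 96.88/20 = 4.844, SE 2.201, power 60.0%. Model, all dropouts scanned: ρ = 0.5 gives 96.88 × (0.75/20 + 0.25/25) = 4.602, SE 2.145, power 62.2%; ρ = 0.8 gives 96.88 × (0.36/20 + 0.64/25) = 4.224, SE 2.055, power 66%.

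**5. Bias when dropout depends on the 1-year change.** Simulated with a true 5-year difference of 5 mm³ unless stated; patients with more loss at 1 year leave more often, except in the last row, where the direction is reversed in one arm.

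| Assumed dropout | Error of the completer difference |
|---|---|
| Same logistic rule in both arms (0.7–1.4 log-odds per SD), 1-year difference 2.5–5 mm³ in the same direction; arm rates 22%/18% to 26%/14% | understated by 0.08–0.66 mm³ |
| Same logistic rule (1 log-odds per SD), 1-year difference 3 mm³ in the opposite direction | overstated by 0.17–0.27 mm³ |
| Same rule, but dropout levels off at 25–30%; 1-year difference 5 mm³ | overstated by 0.05–0.12 mm³ |
| Same rule, no true difference | none; type I error about 5% |
| Rule acts in one arm only, no true difference | about 0.65–1.05 mm³ |
| Rule acts in opposite directions in the two arms, no true difference | about 1.2–1.9 mm³ |

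With all dropouts scanned at 1 year, the model is within about 0.03 mm³ of the truth. In the first row with only half scanned, its error is 0.03–0.25 mm³. The largest error in that row is 0.66/1.74 = 0.4 SE.

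**6. Where the model falls short.** If dropout depends on the 5-year value itself (1 log-odds per SD), the completer error is 0.55–0.58 mm³ and the model's 0.20–0.48 mm³.

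**The case against.** The strongest reply is that a t-test fixes the comparison and not the handling of missing values. A t-test after multiple imputation would use the 1-year scan. The protocol refers to a pre-established analysis plan that is not shown, and its phrase about terms of models may mean that models are planned there. This stands as a condition: the point holds only if nothing is imputed. It does not remove the point, because the protocol names a t-test for its primary outcome and mentions no imputation.

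It is also fair that nothing in the protocol links leaving the trial to CBCT volume, so the mechanisms in step 5 are assumptions. Safeguards exist: patients unable to commit to 5 years, and referred patients who cannot be followed at the centre, are excluded. Recall is six-monthly, investigators may not exclude included patients, dropouts are reported by group, and volume is measured after early failure. These lower the risk but do not bring the 1-year scan of a lost patient into the 5-year contrast.

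A reader might infer more than the documents support:

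- *That the t-test is wrong or the trial loses its planned power.* It is valid if loss is unrelated to outcome, and the 80 patients already include the 20% allowance.
- *That the intention-to-treat promise is broken.* That sentence concerns adherence, not loss to follow-up.
- *That completers always understate the difference once the arms differ at 1 year.* Step 5 shows both directions. The Introduction contrasts a graft that preserves volume with one that is resorbed and replaced, so different time courses are possible.
- *That no true difference means no bias.* This needs the same dropout rule in both arms.

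**Conclusion.** The point holds as a low-cost improvement to the 5-year volume contrast, not as an error. The 1-year contrast is unaffected, because its t-test already uses every 1-year scan.

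The precision gain is modest: about 1.5 to 5 power points at 40 per arm and 2 to 6 at 25 per arm if every dropout was scanned at 1 year, less if half were, and nothing if none were. The better reason for the change is protection against loss related to the 1-year result. That bias is roughly 0.1 to 0.7 mm³ on 5 mm³ under one rule for both arms, of either sign, and larger if the rule differs by arm.

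All sizes rest on the assumed correlation and on assumed dropout timing and mechanism. The figures in the protocol fix only the SD, the difference, the group sizes and the 20%.

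**What to change.** Make the main analysis of volume change a repeated-measures model on all randomised patients with at least one post-baseline CBCT. Its terms are treatment, visit and treatment×visit, with unstructured covariance and small-sample degrees of freedom (Kenward-Roger or Satterthwaite). Report the difference and 95% CI at 1 and at 5 years. Keep the independent-sample t-test as a sensitivity analysis. Write this in before the 5-year data are seen, so that the choice is not post hoc.

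The cost is analysis wording only: no extra visit, scan or patient, and the planned 80 does not change. There are limits to state alongside it. The model relies on missing-at-random. It does not recover patients lost before 1 year. It only reduces the bias if loss depends on the 5-year value itself. It can cost up to about half a point of power if no dropout was scanned at 1 year.

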Official Title:

A resorbable versus a non-resorbable bone substitute at immediate post-extractive single implants immediately loaded: a multicentre randomised controlled trial

Brief Title:

Resorbable vs non-resorbable bone substitute at immediate post-extractive single implants

NCT Number:

NCT07047131

Unique Protocol ID:

2301201902319

Date of the Document:

December 18, 2018

A resorbable versus a non-resorbable bone substitute at immediate post-extractive single implants immediately loaded: a multicentre randomised controlled trial

Introduction

A systematic review did not show statistically significant differences between immediate, immediate-delayed and delayed implant placement protocols in terms of performance due to the poor quality of the available clinical data and underpowered study designs(1). The use of bone substitute can improve aesthetics at post-extractive implants(2). Bone substitutes can be poorly resorbable (semi-degradable), meaning they simply preserve bone volume being integrated into newly-formed bone or can be rapidly resorbed (fully degradable) and replaced by new autogenous bone. It is currently unknown if one of the two mechanisms is preferable at immediate post-extractive implants.

Aims

To compare the effectiveness of a partly versus a fully resorbable bone substitute at immediate post-extractive single implants.

Study Design

Multicentre, single blind, randomised controlled trial of parallel group design where a partly resorbable bone substitute (Apatos) will be compared to a fully resorbable bone substitute (GTO) to fill bone-to implant gaps at immediate post-extractive implants.

Each patient will provide only one implant site. For patients with multiple teeth to be extracted, the operator will be free, at the screening visit, to select one future implant site to be included in the trial. The trial will have a duration of 5-year post-loading.

- Randomisation: using computer generated random numbers, centralized with sequentially sealed opaque envelopes provided by the study adviser ([name]).
- Allocation concealment: the operator will know about the type of graft to place at the implant to bone gap by opening a sealed envelope after the immediate implant has been placed and definitively included in the study.
- Blinding: independent and blind assessors will assess implant stability. Bone level changes, volumetric change and aesthetic evaluation will be done by a single blinded and independent assessor.

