The principles outlined in the Declaration of Helsinki on clinical research involving human subjects will be adhered to. A written informed consent will be obtained for each patient. The study got the approval of the ethical committee King Juan Carlos University, Madrid, Spain

The trial will be reported according to the CONSORT statement for improving the quality of reports of parallel-group randomized trials (<http://www.consort-statement.org/>).

Inclusion criteria at screening

- Any patient requiring at least one single immediate post-extractive implant.
- At least 18 year old, able to understand and to sign an informed consent

- There must be sufficient bone to allow the placement of at least a 3.5 mm diameter and 8.5 mm long implant.
- After tooth extraction there must be a potential gap of at least 2 mm from the buccal inner bone plate and the implant surface.

Exclusion criteria at screening

- General contraindications to implant surgery.
- Immunosuppressed or immunocompromised patients.
- Patients irradiated in the head and/or neck.
- Uncontrolled diabetes.
- Pregnancy or lactation.
- Active periodontal disease
- Poor oral hygiene and motivation.
- Addiction to alcohol or drugs.
- Psychiatric problems and/or unrealistic expectations
- Patients with an acute infection (abscess) in the site intended for implant placement.
- Patients unable to commit to a 5-year follow-up.
- Patients treated or under treatment with intravenous amino-bisphosphonates.
- patients referred only for implant placement if follow-ups cannot be done at treatment centre.
- Patients participating in other studies, if the present protocol could not be fully adhered to. In case of doubts please contact [name] ([contact]).

Exclusion criteria after tooth extraction

- More than 4 mm in height of missing buccal wall, assessed using the highest peak of palatal wall as reference point.
- Less than 2 mm of space between the inner plate of the buccal bone and the implant surface.

Centre and main operator

King Juan Carlos University, Madrid, Spain

Treating surgeon: [name] [name] ([contact])

Masked local outcome assessor: [name] [name]

Study population and number of patients to be included

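### The continuous outcomes of a trial described as multicentre are compared by a t-test without centre; adding centre to the analysis is a cheap gain in precision

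*Protocol*

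**What the plan says.** Study Design in the protocol describes a "Multicentre, single blind, randomised controlled trial of parallel group design". Randomisation is done "using computer generated random numbers, centralized with sequentially sealed opaque envelopes"; blocks, strata and separate sequences by centre are not mentioned.

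Sample size asks for 80 patients in total, allowing for 20% drop-out, and adds: "We can contribute with 50 patients (25 per group"). The other 30 must therefore come from elsewhere, although Centre and main operator lists one centre only.

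Statistical analysis sets the between-group comparison for continuous outcomes. Volume change, marginal bone level change and pink aesthetic score (PES) "will be compared using an independent sample t-test for pairwise comparisons". Failures and complications are compared by chi-square. Centre appears in neither. The same section promises an estimate, standard error, confidence interval and P-value for every model term, but describes no model that has terms.

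**The concern.** Centres can differ in outcome. Surgeons would differ, and under Materials implant length and diameter are left to the operator. Differences between centres stay in the residual variance of a two-sample t-test. If each centre splits its patients evenly between the arms, those differences cancel from the treatment contrast but not from its standard error. The interval is then wider than it should be and the true type I error falls below 5%. If the split is even only overall, the standard error is right on average, but it includes variation that a centre term would remove.

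At stake is the precision of the primary comparison. The sample size leaves little slack: the power at the planned number of completers is just above 80%.

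**Working it through.** **Inputs from the protocol (Sample size):** "To detect a difference of 5 mm³ in bone volume changes between the two bone substitutes"; "standard deviation of 6.96 mm³"; "with a two-side 5% significance level and a power of 80"%; 80 patients with 20% drop-out.

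**Assumptions, because the protocol gives no figures:** two centres of 50 and 30 patients; drop-out equal across arms and centres, leaving 20+20 and 12+12 completers (32 per arm); a range of centre differences.

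**1. The plan's own figure.** The exact t-test calculation gives 31.4 per arm, so 32. Then 2 × 32 = 64, and 64 / 0.8 = 80. The stated total is reproduced. Power at 32 per arm is 80.75%. The standard error is 6.96 × √(2/32) = 1.74 mm³.

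**2. Reading A: 6.96 mm³ is the SD within a centre.** Centre variation comes on top. With balance inside both centres and a centre difference D, the expected t-test variance is

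6.96² + 64 × 0.625 × 0.375 × D² / 62 = 48.44 + 15 D² / 62.

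- D = 0.5 SD = 3.48 mm³: 48.44 + 2.93 = 51.37, so the SE is √51.37 × 0.25 = 1.79, against 1.74 with centre in the model.
- D = 1 SD = 6.96 mm³: 48.44 + 11.72 = 60.16, so the SE is √60.16 × 0.25 = 1.94, against 1.74.

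Simulation (100,000 runs per cell; mean simulated SEs 1.78 and 1.93, against 1.73):

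| Balance | Centre difference | Type I error, t-test | Power, t-test | Power, with centre |
|---|---|---|---|---|
| Within centres | 0 | 5% | 81% | 81% |
| Within centres | 0.5 SD | 4.4% | 79% | 81% |
| Within centres | 1 SD | 3% | 74% | 81% |
| Overall only | 0 | 5% | 81% | 80% |
| Overall only | 0.5 SD | 5% | 78.5% | 80% |
| Overall only | 1 SD | 5% | 72% | 80% |

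With balance only overall and no centre difference, the centre term costs 0.6 to 0.7 points of power.

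**3. Reading B: 6.96 mm³ is the total SD.** Let a share ρ of that variance lie between centres, with balance inside every centre. The t-test SE stays at 1.74 and the correct SE is 1.74 × √(1−ρ), so the t-test SE is too wide by the factor 1/√(1−ρ). By normal approximation (which gives 82.0% power at ρ = 0):

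- type I error = 2 × [1 − Φ(1.96/√(1−ρ))]
- power of the t-test = Φ[(5 − 1.96 × 1.74) / (1.74√(1−ρ))]
- power with centre = Φ[5 / (1.74√(1−ρ)) − 1.96]

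| ρ | SE too wide by | Type I error | Power, t-test | Power, with centre | 95% CI half-width, t-test / with centre (mm³) |
|---|---|---|---|---|---|
| 0.01 | 0.5% | 4.9% | 82.1% | 82.3% | 3.41 / 3.39 |
| 0.05 | 2.6% | 4.4% | 82.6% | 83.8% | 3.41 / 3.32 |
| 0.10 | 5.4% | 3.9% | 83.2% | 85.7% | 3.41 / 3.24 |
| 0.20 | 11.8% | 2.8% | 84.6% | 89.5% | 3.41 / 3.05 |

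With balance only overall, simulation at a centre difference of 5 mm³ (12% of the total variance) gives a mean t-test SE of 1.74 against a true 1.73 and a type I error of 4.7%. Power is 80.8% without centre and 85.1% with it.

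**The case against.** A reader might infer that the reported standard error, interval and P-value will be wrong whenever centres differ. The protocol does not support that. The 25:25 split is one centre's planned contribution. Nothing is said about the split elsewhere, and no blocking or stratification is described. Without balance within centres the t-test's standard error is right on average and its type I error is about 5%.

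A reader might also infer that every between-group comparison is a t-test. That is not so: the dichotomous outcomes use chi-square.

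Other points on that side:

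- **Only one centre is named.** If its patients are analysed alone, there is no centre effect to leave out. This stands.
- **The protocol does not call 6.96 mm³ a within-centre SD.** On the total-SD reading the planned 80% is met without adjustment. This stands, and it removes any claim of a certain power shortfall.
- **A 1 SD centre difference is large.** At about 7 mm³ it exceeds the 5 mm³ treatment effect sought. It marks the upper end of the range shown, not an expected value.
- **Design features limit centre effects.** One blinded assessor reads volume, bone level and aesthetics, the implant system and graft products are fixed, and two of the three continuous outcomes are changes from baseline. These reduce centre effects but do not rule them out, since surgical technique can affect the change itself.
- **Covariates may be left to the analysis plan, which is not shown.** This stands only in part. The protocol itself names the test for the primary outcome, and a centre-adjusted model in the plan would differ from it.

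**Conclusion.** This is a cheap improvement, not a demonstrated error. The t-test named for the continuous outcomes leaves out centre in a trial described as multicentre. If allocation is balanced within centres and centres differ, the test is conservative. If it is balanced only overall, the test is valid but less precise than it could be. In neither case is the treatment estimate biased or the false-positive rate raised.

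On the two-centre assumption with 6.96 mm³ as the within-centre SD and balance within centres, the loss is about 2 points of power at a 0.5 SD centre difference and about 7 points at 1 SD. With 6.96 mm³ as the total SD, planned power is kept and the cost is a somewhat wider interval, for example a half-width of 3.41 instead of 3.24 mm³ when centre accounts for 10% of the variance. The number of centres, their sizes and the centre effect are all assumed. With one centre the point lapses.

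**What to change.** - Under Statistical analysis, replace the t-test for volume change, marginal bone level change and PES with a linear model that has treatment and centre as fixed terms. Report the centre-adjusted mean difference with its 95% confidence interval. This also gives the existing promise to report each model term something to refer to.
- Under Study Design, state whether the envelope sequence is balanced by centre.

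The cost is a sentence or two of text, one degree of freedom per extra centre, and under 1 point of power if centres turn out not to differ. If only one centre enrols, the centre term drops out and the model is the t-test already planned.
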